5. STUDY OUTCOMES

5.1 Co-primary outcomes

1.1: Time (days) to normalization of all VS for at least 24h (efficacy)

Defined as T <38.0°C, RR and HR within age-specific reference ranges, and SpO₂ on room air ≥93% (Table 1).

Table 1. Reference values for body temperature (T), respiratory rate (RR), heart rate (HR), and saturation of peripheral oxygen (SpO₂) on room air.

Vital sign (VS):	Body temperature (T)	Respiratory rate (RR)	Heart rate (HR)	Saturation of peripheral oxygen (SpO ₂) on room air
Specific measurement:	Ear thermometer	Clinical assessment or parental report	Pulse oximetry (mobile device for ambulatory patients)	Pulse oximetry (mobile device for ambulatory patients)
Unit:	°C	Breaths/min	Beats/min	%
Reference:	[7]	[61]	[61]	[8]
3 years	<38.0	21-29	86-123	≥93
4-5 years		20-27	81-117	
6-7 years		18-24	74-111	
8-11 years		16-22	67-103	
12-14 years		15-21	62-96	
15-17 years		13-19	58-92	

The specific variables and age-specific reference values will appear in the patient self-documentation in secuTrial® or study diary.

Specific measurement: VS will be measured before randomization (or prior to the administration of antipyretic medication at the ED). These VS measurements will be taken as the index time point for the assessment. VS will be measured after having the patient relax (without running, crying, etc. for at least 5min) every 8h (for hospitalized patients) or 3x/24h (for ambulatory patients) until 3 consecutive normal measurements of *all* VS (T, RR, HR, and SpO₂) within 24h are documented.

Analysis metric: Time to event (days).

Method of aggregation: Hazard/median time to event.

Time point: Time point of the last of 3 consecutive normal measurements of all VS within 24h.

Rationale: The resolution of all VS abnormalities has been proposed as an important primary endpoint for antibiotic trials in childhood pneumonia by the IDSA [62]. In contrast to adults, severe morbidity and mortality from CAP is minimal in children, particularly for *Mp* CAP (section 3.5 and 3.7). Previous trials on macrolides for *Mp* CAP have mainly focused on fever duration as a key endpoint [31, 32]. In the myCAP study, the median body temperature (T) at presentation among myCAP patients was 39.1°C (IQR, 39.0-39.7), and the clinical diagnosis of CAP based on fever and tachypnea could be radiologically confirmed in 98% of the cases [43]. On room air, 17% *Mp* CAP patients had an SpO₂<93% and required additional oxygen supply. The median fever duration for *Mp* CAP children was 2 days. There were no statistically significant differences between patients with or without antibiotic treatment for *Mp* [43]. Lu et al. [63] observed a mean fever duration of 5 days (no statistically significant differences between patients treated with macrolides or placebo). To conclude, this study will use VS measurements taken at the timepoint before randomization as baseline measurements. The VS measurements will be followed up until normalization of VS to reference values. We expect a rate of <1% of patients' VS not normalizing within a 28-day FUP. In agreement with the IDSA considerations [62], an assessment of the time to VS normalization (T, RR, HR, SpO₂) has been selected to be of main interest for MYTHIC.

1.2: CAP-related change in patient care status within 28 days (safety)

Defined as any change in patient care status from an ambulatory to hospitalized setting (admission or re-admission), or from a hospitalized on general ward to an ICU setting (ICU transfer).

Specific measurement: Incidence of (re-)admission to hospital or transfer to the ICU.

Analysis metric: Final value.

Method of aggregation: Proportion.

Time point: Within 28 days after randomization.

Rationale: We expect the placebo to be non-inferior to macrolides treatment regarding a CAP-related change in patient care status. This non-inferiority will be assessed by the incidence of (re-)admission to

the hospital or transfer to the ICU (safety). A recent U.S. study showed that re-admission occurred in 5% of children with CAP receiving beta-lactam monotherapy and in 2% receiving beta-lactam plus macrolide combination therapy [13]. In another U.S. CAP study, re-admission was reported in 0.5% of those who received beta-lactam monotherapy and in 0.6% of those who received beta-lactam plus macrolide combination therapy [64]. Detailed information about the proportion of patients with *Mp* infection was not available for both studies. Based on these data we expect a small proportion ($\leq 5\%$) of patients with a CAP-related change in patient care status.

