Statistical considerations:	
Multiplicity with two co-primary endpoints was handled using the “at least one” success criterion: We estimated the sample size for both co-primary endpoints for a one-sided significance level of 1.25% and a power of 80%, and use the larger of the two sample sizes for the trial. This assures a minimum power of 80% to reject at least one null hypothesis.
 
The co-primary endpoint time to normalization of all VS is considered as a time-to-event endpoint. The sample size was estimated assuming an overall event rate of 99% and a hazard ratio of 1 for placebo vs. macrolide (a hazard ratio <1 would indicate longer duration with placebo than with macrolide). The sample size was estimated to show the non-inferiority of placebo vs. macrolide in Mp PCR-positive patients using a non-inferiority margin of 0.7 for the hazard ratio. Considering a drop-out rate of 14.5%, 354 patients should be recruited for the intervention phase of this study (302 evaluable patients).
 
For the co-primary endpoint CAP-related change in patient care status (binary) we expect an absolute risk of 5% in both trial arms and thus an absolute risk difference (ARD, $risk_{macrolide} - risk_{placebo}$) of 0 between the two arms. An ARD <0 would indicate a higher risk with placebo than macrolide. The sample size was estimated to show the non-inferiority of placebo vs. macrolide in Mp PCR-positive patients, using a non-inferiority margin of -7.5% for the ARD. Considering a drop-out rate of 14.5%, 376 patients should be recruited for the intervention phase of this study (322 evaluable patients).

GCP statement:	
This study will be conducted in compliance with the protocol, the current version of the Declaration of Helsinki, ICH-GCP, as well as all national legal and regulatory requirements.

ABBREVIATIONS

AE	Adverse event
AESI	Adverse event of special interest
AMR	Antimicrobial resistance
AR	Adverse reaction
ARD	Absolute risk difference
ASC	Antibody-secreting cell
ASR	Annual safety report
BASEC	Business Administration System for Ethical Committees (https://submissions.swissethics.ch/en/)
BTS	British Thoracic Society
CA	Competent authority (e.g., Swissmedic)
CAP	Community-acquired pneumonia
CEC	Competent ethics committee
CI	Confidence interval
ClinO	Ordinance on Clinical Trials in Human Research (in German: KlinV, in French: OClin, in Italian: OSRUm)
CTCAE	Common terminology criteria for adverse events

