7. STUDY POPULATION AND INFORMED CONSENT PROCEDURE

7.1 Eligibility criteria

Inclusion criteria:

Inclusion criteria for screening phase:

- **Children aged 3-17 years** (from 3rd up to 18th birthday) presenting to the ED who will be managed ambulatory or will be admitted to general ward.
- **Clinical diagnosis of CAP:**
 - 1) **Diagnosis defined as the treating physician's documented diagnosis of CAP;** AND
 - 2) **Fever $\geq 38.0^{\circ}\text{C}$** (measured by any method [i.e., ear, axillary, rectal, or forehead site] in the ED or via parent report observed in the last 24h); AND
 - 3) **Tachypnea** (RR above the age-specific reference value as defined in section 5.1, Table 1 during the assessment in ED [triage or clinical examination]).

This trial aims to produce translational results generalizable to a “real-world” setting. In ED settings, the diagnosis of CAP is generally based on clinical criteria [8, 9]. Therefore, inclusion criteria for this study will not be based on radiological or laboratory diagnostics. However, according to our experience from previous studies and feedback from participating centers, we expect $\geq 90\%$ of children to have a CXR performed as part of their diagnostic routine.

- **Written screening consent for participation in screening phase** signed by parents or legal guardians and the patient if ≥ 14 years of age.

Additional inclusion criteria for intervention phase:

- **Positive *Mp* screening test result** with the *Mp* IgM LFA (grade 2 or 3) (section 6.1).
- **Written informed consent for participation in intervention phase** signed by parents or legal guardians and the patient if ≥ 14 years of age.

Exclusion criteria:

Exclusion criteria for screening phase:

- None.

Exclusion criteria for intervention phase:

- Contraindication to azithromycin: Documented allergy to azithromycin; cardiovascular disease, including bradycardia, arrhythmias, and/or QT-interval prolongation*; myasthenia gravis.
*Co-medication with arrhythmogenic or QT-interval-prolonging drug (<https://crediblemeds.org>) is no exclusion criteria but will be discussed with the local investigators and/or TMT.
- Underlying comorbidities: Cystic fibrosis or other chronic lung disorders (excluding asthma), primary or secondary immunodeficiency, sickle-cell anemia, or severe cerebral palsy.

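### Normalization of RR and HR is judged against a two-sided range, so a recovered child with a low resting rate counts as not normalized; the bias towards non-inferiority is small unless low readings cluster strongly within children

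*Protocol*

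**What the plan says.** Section 5.1 of the protocol defines co-primary outcome 1.1 as body temperature below 38.0°C, "RR and HR within age-specific reference ranges", and SpO2 on room air of at least 93%. Table 1 gives two limits for each rate, for example RR 21-29 and HR 86-123 at age 3, and RR 13-19 and HR 58-92 at 15-17 years. No section says that a value below the lower limit counts as normal.

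- **Event time:** "Time point of the last of 3 consecutive normal measurements of all VS within 24h".
- **Measurement:** "VS will be measured after having the patient relax" for at least 5 minutes, every 8 hours in hospital and three times per 24 hours at home. Measurement stops once three consecutive normal sets are documented (also sections 9.2.1, 9.3.5 and 9.3.6.1).
- **Entry:** section 7.1 defines tachypnea as "RR above the age-specific reference value as defined in section 5.1", so only the upper limit is used. There is no heart-rate criterion for entry.
- **Expected completeness:** section 5.1 expects fewer than 1% of patients with "VS not normalizing within a 28-day FUP", and section 11.2 plans on a 99% event rate.
- **Further use:** in section 5.2, Table 3, a patient without normalization of all vital signs falls in DOOR category 5, 6 or 7, below a patient who normalized but had a severe solicited adverse event (category 4).

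**The concern.** Pneumonia raises RR and HR. A low rate in a resting, recovered child is not a sign of unresolved pneumonia, yet the definition counts it as one. A 3-year-old whose tachypnea settles to an RR of 20, or a 16-year-old with a resting HR of 56, restarts the three-reading count. A child whose rate is habitually low may never reach the event.

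Such readings have nothing to do with treatment and affect both arms. In a superiority trial they would mainly cost power. Here noise that pulls the hazard ratio towards 1 makes a truly slower recovery on placebo look more acceptable, so the error runs in the anti-conservative direction. Section 11.4.2 lets the trial succeed on either co-primary endpoint, so this one can carry the conclusion alone.

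**Working it through.** **1. The plan's own figures.** Inputs from section 11.2 and the synopsis: margin 0.7, expected hazard ratio 1, 1:1 allocation, sizing "for a one-sided significance level of 1.25% and a power of 80"%, 99% events, 14.5% drop-out.

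- Events = 4 × (2.2414 + 0.8416)² / (ln 0.7)² = 4 × 9.505 / 0.1272 = 298.9.
- Evaluable = 298.86 / 0.99 = 301.9, so 302. Enrolled = 302 / (1 − 0.145) = 353.2, so 354.
- Exponential times with 99% overall events by day 28 give medians of 3.34 and 4.77 days at the margin (stated 3.3 and 4.8) and 4.21 days at a hazard ratio of 1 (stated 4.2).

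The sample size reproduces and is not in question.

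**2. Simulation model.** True recovery is exponential with a hazard ratio of 0.70. Readings are 8-hourly, the event is the third consecutive normal reading, and follow-up is censored at day 28. After recovery, a reading of each rate falls below its lower limit with a probability that is the same in both arms. **Assumptions not in the protocol:** that probability (5-10% per sign) and how far it differs between children, taken as beta-distributed with precision s. The within-child correlation is 1/(1 + s):

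- s = 1 gives 0.50 and s = 2 gives 0.33 (strong clustering).
- s = 5 gives 0.17 and s = 10 gives 0.09 (moderate and weak).

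With two independent signs, 5% and 10% per sign mean that 1 − 0.95² = 9.75% and 1 − 0.90² = 19% of reading times fail.

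**3. Chance of wrongly declaring non-inferiority.** Φ( ln(HR_obs/0.7) × √(302 × e/4) − 2.2414 ), where e is the observed event proportion.

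**4. Results at 5-10% low readings per sign, N = 302.**

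| Low readings | Observed HR | False non-inferiority |
|---|---|---|
| None (upper limit only) | 0.70 | about 1.2-1.3% |
| No, weak or moderate clustering (s ≥ 5) | 0.70-0.72 | 1.1-2.3% |
| Strong clustering (s = 1-2) | 0.74-0.81 | 3.4-13.9% |

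Values of 1.1-1.2% are the nominal 1.25% within simulation error. A separate run of this model with 322 children gave at most 2.7% at s = 5 and 1.4-1.5% at s = 10.

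**5. Cross-check with one combined probability q per reading time and correlation 0.3.** For q = 5%, 10%, 20% and 30% the hazard ratio is 0.714, 0.727, 0.768 and 0.804, and false non-inferiority is 1.9%, 2.7%, 7.3% and 13.9%. For q = 20%, with e = 0.955: ln(0.768/0.7) = 0.0927; √(302 × 0.955/4) = 8.49; 0.0927 × 8.49 − 2.2414 = −1.454; Φ = 7.3%.

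With independent readings, q = 30% moves the hazard ratio only to 0.706, but the medians (azithromycin/placebo) lengthen from 4.0/5.7 to 5.3/7.0 days. At a true hazard ratio of 1 with clustered low readings it stays at about 1 (1.005).

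**6. Event rate.** With s = 5-10, non-events are 1.1-1.8% against the planned 1%. With strong clustering they are 2.5-8.6%.

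**The case against.** The strongest objection is that the size depends on clustering, about which the protocol says nothing. The strong-clustering scenarios imply that roughly 4-15% of children have more than half of their RR or HR readings below the limit. At moderate clustering the effect on the error rate largely disappears. This stands: the upper figures are a pessimistic end, not a central estimate.

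Three stronger readings are tempting, and the document does not support them.

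- **Entry and outcome contradict each other.** They do not. Tachypnea at entry serves to diagnose pneumonia; the outcome is return to reference values, a broader construct that the protocol states consistently. The difference shows that the lower limit adds something unrelated to the illness that qualified the child. It is not an internal error.
- **Sleeping children are counted as ill.** The 8-hourly inpatient schedule makes night readings likely, but sleep is never mentioned, and the rest instruction reads naturally as an awake child. Home readings have no fixed night time, and only 32% of *Mp* CAP patients in the earlier cohort were hospitalized (section 3.5). Sleep is an inference; rest is explicit.
- **The 99% event rate is wrong.** It comes under clear pressure only with strong clustering.

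It can also be said that the recorded values allow a one-sided analysis later. That is true and makes the fix cheap, but the primary definition should still be settled in advance.

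**Conclusion.** The point holds as a weakness of endpoint definition. A low resting RR or HR in a recovered child delays or blocks a co-primary event in both arms and worsens that child's DOOR category. The direction of any bias in the hazard ratio is towards 1, which is anti-conservative here.

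Its size is uncertain. At 5-10% low readings per sign it is slight with no to moderate clustering (about 1.1-2.3% false non-inferiority against 1.25%) and material only with strong clustering (about 3-14%). Both inputs are assumptions. A reader might infer that the type I error is badly inflated; the protocol does not support that, and the sample size of 302 evaluable and 354 enrolled for this endpoint is unaffected. The change is worth making because the lower limits add nothing to the measurement of recovery and removing them is nearly free.

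**What to change.** In sections 5.1 and 9.2.1, define the co-primary event as three consecutive readings within 24 hours with T <38.0°C, RR and HR not above the age-specific upper limit of Table 1, and SpO2 on room air ≥93%. Use the same definition for adequate clinical response in Table 3 (DOOR).

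Derive the event from the recorded values and leave the measurement-stopping rule in the diary and secuTrial as it is. Every reading that meets the two-sided rule also meets the one-sided rule, so the one-sided event never comes later and is always captured. If measurement stopped at the one-sided event instead, the two-sided event would go unobserved in exactly the children at issue. Keep the two-sided version as a sensitivity analysis.

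The cost is outcome wording and one derivation rule, with no new measurements and no change to the sample size. The small downside is that an abnormally low rate alone no longer delays the event.

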5.2 Secondary outcomes

A number of secondary and additional outcomes have been defined as relevant endpoints for antibiotic trials in childhood CAP by the IDSA [62].

2.1: Overall clinical outcome based on benefits and harms (DOOR/RADAR approach)

According to documentation of clinical response (normalization of all VS) and solicited AEs 1x/24h at the end of treatment (day 5) and each FUP visit.

Specific measurement: Documentation of clinical response (normalization of all VS, section 5.1) and solicited AEs (Table 2) 1x/24h at the end of treatment (day 5) and at each FUP visit.

Analysis metric: Desirability of outcome ranking (DOOR) [65].

Method of aggregation: Probability of better DOOR.

Time point: Day 3 (in-hospital visit), day 5 (end of treatment), day 7, 14, 21 (phone calls), and day 28 (close-out visit).

Rationale: The novel *response adjusted for duration of antibiotic risk* (RADAR) methodology utilizes a superiority design [65]. In RADAR, all trial participants are assigned a DOOR. The DOOR is constructed using a 2-step process: (1) categorization of all patients into an overall clinical outcome (Table 3), and (2) ranking participants in the trial using 2 rules: (2a) when ranking the outcomes of 2 patients with different overall clinical outcomes, the patient with a better overall clinical outcome receives a higher rank; and (2b) when ranking the outcomes of 2 patients with the same overall clinical outcome, the patient treated with placebo receives a higher rank. These DOOR ranks are then compared between the treatment arms with regard to the probability of a better DOOR for a randomly selected patient with placebo vs. azithromycin (i.e., Wilcoxon-Mann-Whitney statistic [66]). The DOOR/RADAR approach is helpful for RCTs to define the optimal therapeutic strategy, since considering exclusively the primary endpoint may not allow researchers to accurately balance a proven benefit with other potential harms (i.e., impaired effectiveness or side effects/AEs).

Table 2: Solicited adverse events (AEs) grading [66, 67].

Symptom	Mild (grade 1)	Moderate (grade 2)	Severe (grade 3)
Diarrhea	Looser than normal stools occurring 3-6 times/day	Looser than normal stools occurring >6 times/day	Bloody diarrhea, or diarrhea that requires medical intervention, laboratory testing, or hospitalization
Vomiting	1 episode/day	2-3 episodes/day	≥ 4 episodes/day
Abdominal pain	Mild or intermittent and does not interfere with daily activity	Moderate or persistent and interferes with daily activity but did not need a medical visit or absenteeism from daily routine	Prevents daily activity and resulted in medical visit or absenteeism
Allergic reaction (rash and/or pruritus)	Localized rash or pruritus without rash	Diffuse rash (maculopapular or urticarial)	Generalized rash consistent with Stevens-Johnson syndrome, erythema multiforme, or toxic epidermal necrolysis; anaphylaxis; or angioedema
Oral/pharyngeal thrush or nappy rash (Candidiasis)	Mild mucocutaneous candidiasis or diaper dermatitis, with no treatment or topical treatment only	Moderate mucocutaneous candidiasis requiring oral antimicrobial treatment	Severe mucocutaneous candidiasis; requires medical intervention, intravenous treatment, or hospitalization

Table 3: Overall clinical outcome.

Outcome	Adequate clinical response*	Solicited AEs**
1	Yes: normalization of all VS	No
2	Yes: normalization of all VS	Mild (grade 1)
3	Yes: normalization of all VS	Moderate (grade 2)
4	Yes: normalization of all VS	Severe (grade 3)
5	No: no normalization of all VS without additional ED or clinic visit or hospitalization	Any grade
6	No: no normalization of all VS with additional ED or clinic visit but without hospitalization	Any grade
7	No: no normalization of all VS with hospitalization (admission, re-admission, or ongoing hospitalization)	Any grade
8	Death (any cause)	

* Adequate clinical response defined by the co-primary outcome normalization of all VS (section 5.1).

** Solicited AEs are defined in Table 3.

2.2: Time (days) to normalization of CAP-related symptoms (i.e., cough, shortness of breath, wheeze, chest pain, sore throat, nasal congestion or runny nose, headache, muscle aches or pains, nausea or vomiting, diarrhea, reduced general condition, decreased appetite, not sleeping well, reduced activity).

Specific measurement: Documentation of symptoms 1x/24h according to a validated measure for childhood respiratory infections [68, 69] by parent and the child until normalization.

Analysis metric: Time to event (days).

Method of aggregation: Hazard/median time to event.

Time point: Time point of resolution of all CAP-related symptoms.

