5.4 Safety outcomes

The main outcomes regarding safety include the co-primary outcome (1.2, CAP-related change in patient care status), secondary outcomes (2.1, overall clinical outcome based on benefits and harms, and 2.5, development of *Mp*-associated extrapulmonary manifestations), and additional outcomes in section 5.3, such as unscheduled medical visits, (re-)treatment with antibiotics, and side effects/AEs/SAEs of IMP.

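### DOOR Table 3 counts hospitalization only while vital signs are abnormal, so at the late visits the outcome is nearly blind to CAP-related admission and ICU transfer

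*Protocol*

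**What the plan says.** Outcome 2.1 (Protocol section 5.2) sorts every child into the eight categories of Table 3 and then compares ranks between arms.

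- Categories 1-4 share one entry condition, "Yes: normalization of all VS", and differ only in the grade of solicited AEs. Table 2 lists these as diarrhea, vomiting, abdominal pain, allergic reaction and candidiasis.
- Categories 5-7 all require that VS have not normalized. They are separated by no extra visit, an ED or clinic visit, or hospitalization. Category 7 reads "No: no normalization of all VS with hospitalization (admission, re-admission, or ongoing hospitalization". Category 8 is death.
- The footnote leaves no room for other criteria: "Adequate clinical response defined by the co-primary outcome normalization of all VS (section 5.1".
- The time points are "Day 3 (in-hospital visit), day 5 (end of treatment), day 7, 14, 21 (phone calls), and day 28 (close-out visit".
- Ties go to placebo: "when ranking the outcomes of 2 patients with the same overall clinical outcome, the patient treated with placebo receives a higher rank". Section 11.4.3 repeats this rule and adds a second analysis without it.

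Sections 9.2.2 and 11.4.3 add no criterion for admission or ICU transfer. Section 5.4 nevertheless names the "overall clinical outcome based on benefits and harms" among the main safety outcomes, and sections 9.2.4 and 11.4.5 list it again.

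**The concern.** In a trial that withholds an antibiotic, the harm of most interest is deterioration that leads to admission or intensive care. Section 5.2 justifies the DOOR by the need to weigh benefit against impaired effectiveness as well as side effects. Under Table 3, impaired effectiveness counts only while VS are abnormal. Once they have normalized, a child who has been through intensive care and has no solicited AE is in category 1, the best one. If that child received placebo, the tie rule ranks the child above every never-admitted azithromycin child in category 1.

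At stake is how the late-visit DOOR results are read. A neutral or favourable value at day 28 could be taken as evidence of overall safety when the ranking could hardly have shown a difference in admissions.

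**Working it through.** **Inputs from the Protocol.** Enrolled: 376 (section 11.2). Expected risk of a change in care status: 5% per arm. Highest placebo risk allowed by the margin: 12.5% (section 11.2). Normalization: "We expect a rate of <1% of patients' VS not normalizing within a 28-day FUP" (section 5.1). Median time to normalization at a hazard ratio of 1: 4.2 days, exponential (section 11.2).

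**The plan's own figure.** No sample size or expected value is given for the DOOR. The trial size comes from the binary co-primary endpoint: n per arm = (2.2414 + 0.8416)² × 2 × 0.05 × 0.95 / 0.075² = 160.5, so 161 per arm and 322 in total, as stated. Then 322 / 0.855 = 376.6, against 376 stated.

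**Which visits are affected.** Under the plan's exponential assumption, the share not normalized at day t is 0.5^(t/4.2).

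| Day | 3 | 5 | 7 | 14 | 21 | 28 |
|---|---|---|---|---|---|---|
| Not normalized | 61% | 44% | 31% | 10% | 3% | 1% |

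Categories 5-7 are well filled in the first week and almost empty at days 21-28.

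**Children concerned at day 28.** Expected care-status changes: 0.05 × 376 = 18.8. Not normalized: fewer than 0.01 × 376 = 3.76. Even if every non-normalized child were also a care-status case, at least 18.8 − 3.76 ≈ 15 of the 19 would be in categories 1-4.

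**Effect on the summary measure at day 28.** Write B for the probability that a placebo child is in a better category than an azithromycin child, and T for the probability of the same category. Without the tie rule the measure is B + T/2; with it, B + T.

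Assume care-status risks of 12.5% (placebo) and 5% (azithromycin), equal AE rates, and 1% not normalized, placed in category 7. When the event is counted, it also goes to category 7. With no AEs:

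- As written, both arms are 0.99 / 0.01. B = 0.0099 and T = 0.9802, giving 0.500 without the tie rule and 0.990 with it.
- Event counted, placebo is 0.875 / 0.125 and azithromycin 0.95 / 0.05. B = 0.875 × 0.05 = 0.04375; T = 0.83125 + 0.00625 = 0.8375. This gives 0.4625 without the tie rule and 0.881 with it.

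| Solicited AE rate (placebo / azithromycin) | Tie rule | As written | Event counted |
|---|---|---|---|
| 0% / 0% | no | 0.500 | 0.4625 |
| 0% / 0% | yes | 0.990 | 0.881 |
| 10% / 10% | no | 0.500 | 0.4625 |
| 10% / 10% | yes | 0.902 | 0.806 |
| 20% / 20% | no | 0.500 | 0.4625 |
| 20% / 20% | yes | 0.833 | 0.748 |
| 5% / 10% (all normalized) | no | 0.525 | 0.483 |
| 5% / 10% (all normalized) | yes | 0.955 | 0.844 |

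The last pair works out as follows.

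- As written: B = 0.95 × 0.10 = 0.095; T = 0.855 + 0.005 = 0.86.
- Event counted: placebo 0.831 / 0.044 / 0.125, azithromycin 0.855 / 0.095 / 0.05. B = 0.1227; T = 0.7211.

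In the as-written column the care-status risks do not enter at all. An excess at the full margin leaves the day-28 result unchanged.

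**The case against.** **The event is not lost to the trial.** Change in care status is co-primary outcome 1.2, with its own margin, and section 5.4 lists it first among the safety outcomes. No primary conclusion or sample size rests on the DOOR. This stands and limits the weight of the point.

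**Early visits do register it.** A reader might infer that an admission never leaves a trace in the DOOR. The Protocol does not support that. A child in hospital with abnormal VS at day 3, 5 or 7 is in category 7. Section 9.2.1 ties a CAP-related (re-)admission to the inclusion signs, fever and tachypnea among them, so VS are abnormal when it happens. Day 28 is not named as the main DOOR time point. The gap therefore belongs mainly to days 21-28.

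**No general change of direction.** The row with 5% versus 10% AEs and no tie rule moves from 0.525 to 0.483, and a reader might infer that the conclusion reverses. That analysis is only the additional one in section 11.4.3. Its AE rates are assumed: section 3.6 gives rates for single events on azithromycin, but no overall rate and none for placebo. Under the planned tie rule the same inputs give 0.955 and 0.844, both in favour of placebo.

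**No proven tilt from the AE items.** A reader might also infer that the late DOOR measures nothing but macrolide side effects. Vomiting and diarrhea are also listed CAP symptoms under outcome 2.2. Grade 3 allergic reaction includes Stevens-Johnson syndrome, which section 9.2.2 lists as a possible *Mp* manifestation. Some harm from untreated disease can therefore enter categories 2-4. The Protocol does not say whether AEs at a visit are current or cumulative.

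**A careless remedy could do damage.** If every admission counted, the index admission would fix the rank of children hospitalized at entry; section 3.5 reports 32% hospitalized among *Mp* CAP patients. If every clinic visit counted, a recovered child with one visit would rank below a child who never normalized. Both objections stand and shape the fix.

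**Conclusion.** The point holds for the later time points. Table 3 makes the DOOR nearly blind at days 21-28 to the harm that co-primary outcome 1.2 measures, although the DOOR is a listed safety outcome meant to weigh benefits and harms together. On the plan's own expectations, at least about 15 of 19 children with a change in care status would be ranked at day 28 on solicited AE grade alone.

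With 12.5% versus 5% care-status change and equal AE rates, counting the event moves the probability of a better outcome on placebo from 0.500 to about 0.46 without the tie rule. With the tie rule the value falls by about 0.09 to 0.11 but stays above 0.5. These figures assume 99% normalized at day 28, the remaining 1% in category 7, and the AE rates shown. The structural finding needs none of these assumptions beyond the plan's own figure of fewer than 1% not normalized.

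The categories are fixed in the Protocol, so an analysis plan that adopts Table 3 takes the gap with it. The change should be made, but the primary conclusions do not depend on it.

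**What to change.** Amend Table 3 before unblinding:

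- A CAP-related change in care status as defined for outcome 1.2, occurring after randomization and up to the time point, places the child below categories 1-4 whether or not VS later normalize. This covers a new admission, a re-admission or an ICU transfer.
- The index admission does not count as such an event.
- ICU transfer ranks worse than ward admission and above death.
- ED and clinic visits stay as they are in categories 5-6.

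The simplest wording widens category 7 and adds an ICU category between it and death. The trial team should confirm that it accepts a child who recovered after a new admission ranking below a child still abnormal without one.

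The cost is a rewording of one table. The events are already collected for outcome 1.2, so no new data are needed. On the downside, Table 3 departs slightly from its present form, and the DOOR result may become less favourable to placebo. Fixing the ranking while the data are still blinded avoids any suspicion that it was chosen after the results were seen.
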